A sample size of 8 teams per group was calculated from a published abstract to detect a 3 ml/sec improvement in the rate of fluid administration (power=0.08, alpha 0.05). Nine teams per group (total of 27 teams) were enrolled due to concerns about the study functioning per protocol. Descriptive data are shown as median (interquartile range) and mean (SEM). The distributions of the outcome variables were normal and results from parametric tests are presented. Differences between 2 groups were also evaluated by comparison of median and mean differences with their associated 95% confidence intervals (CIs). Comparisons involving 3 groups were made with 1-way ANOVA or Kruskal-Wallis tests. Correlation was calculated as a Pearson coefficient. Categorical variables were analyzed with the 2 tailed tests. A P .05 was considered to be significant throughout. All data analysis was completed using SPSS (IBM Corp. Released 2011 IBM SPSS Statistics for Windows, Version 20.0. Armonk, NY: IBM Corp).

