Yale University

Institutional Review Board [name] [contact] [contact]

http://info.med.yale.edu/hic

To:	[name].
From:	Yale Institutional Review Board
Date:	12/21/2016
Committee Action:	Exemption Granted
IRB Action Date:	12/21/2016
IRB Protocol #:	1612018709
Study Title:	Fluid Administration with LifeFlow vs Push/Pull.

Educational Research Conducted in Educational Settings. Research conducted in established or commonly accepted educational settings, involving normal educational practices, such as:i) research on regular and special education instructional strategies, orii) research on the effectiveness of, or the comparison among instructional techniques, curricula, or classroom management methods

Exempt studies do not require annual IRB review. Modifications to exempt research do not need a formal IRB review unless the proposed revision affects the exempt status of the protocol. Such changes may include, but are not limited to, addition of collection of identifiers when the original protocol included anonymous data only, addition of children or prisoners as study subjects, or addition of procedures that could potentially increase risk to subjects. See the Exemption Guidance (100 GD9) for more information and examples.

Whenever an exempt protocol is modified (regardless of the type of change), updated versions of all research documents affected by the change must be sent to the IRB Office for the file. Revisions to the documents must be tracked. Changes that do not require IRB review will not be acknowledged formally.

Investigators are also required to promptly report any unanticipated problems or complaints to the IRB.

Review Comments:

• EXEMPTION 45 CFR 46.101(b)(1) This research is exempt from IRB review under federal regulation 45 CFR 46.101(b)(1). This part of the regulations covers research conducted in established or commonly accepted educational settings, involving normal educational practices such as (i) research on special education instructional strategies, or (ii) research on effectiveness of or the comparison among instructional techniques, curricula, or classroom management methods.

LifeFlow Protocol:

Training:

- Participants are randomized to the device.
- A 5-minute training video is viewed on how to use the device that participants are randomized to.

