- Participants are given the device, a 1L NS bag, tubing and a 22g IV. They will demonstrate ability to set up the device and fill an empty container with fluid.
- For Lifeflow:
 - Box opened, 2 pieces of tubing removed from box.
 - Blue caps taken off and 2 pieces of tubing connected
 - 1L bag spiked and connected to tubing
 - o Device unlocked, opened, and tubing inserted with plunger properly placed
 - Device pointed upward so air rises while device is pumped until primed and air removed from line.
 - Distal tubing connected to IV and participant pumps water through.
 - Participants reminded to change 1L bag when about 2cm fluid remain.
 - Line is changed from first 1L bag to second and device continues to be used.
- For Push/Pull:
 - Tubing, 3-way stopcock, 20cc syringe and 22g IV provided in an equipment box
 - Participants spike bag, connect tubing, and use syringe/stopcock to prime line.
 - Practice changing position of stopcock for fluid to flow through IV
 - Line is changed from first 1L bag to second and device continues to be used
- For Pressure Bag:
 - Tubing, sleeve, and 20 cc syringe provided in an equipment box
 - 1L bag placed in sleeve, spiked and tubing connected to IV.
 - Sleeve pressurized to 300mmHg

Set up:

- 10 kg child with a 22-gauge IV catheter x 2, device and appropriate tubing
- The distal end of the catheter was secured in an unobstructed manner within conduit tubing leading to a graduated cylinder.
- The graduated cylinder, used to collect and measure fluid kept hidden from the view of participants.
- The proximal end of the intravenous catheter was connected via a catheter extension set to the appropriate technique-dependent setup.
- Cameras set up on graduated cylinder and overall resuscitation.

Trial:

- Vitals given to participants indicating septic shock
- Algorithm available indicating 20cc/kg boluses x 3: *Clinical practice parameters for hemodynamic support of pediatric and neonatal septic shock: 2007 update from the American College of Critical Care Medicine. Crit Care Med 2009; 37:666.*
- Heart rate and blood pressure slightly improve after each subsequent bolus
- Participants prompted if necessary to continue giving fluids
- Simulation ends after 15 min, expect to also give antipyretics (Tylenol), can obtain labs and should give antibiotics
 - CHARGE NURSE BRINGS IN ANTIBIOTIC AT TIME= 8 MINUTES
 - Participants timed on setup, infusion of each bolus, total time for 3 boluses

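### The sample-size statement gives a design power of 0.08, which is not credible, and omits the inputs needed to correct it

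*SAP*

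**What the plan says.** The statistical paragraph of the SAP (unnumbered) says that 8 teams per group were calculated from a published abstract "to detect a 3 ml/sec improvement in the rate of fluid administration (power=0.08, alpha 0.05". It continues: "Nine teams per group (total of 27 teams) were enrolled due to concerns about the study functioning per protocol". No other part of the available text states a power.

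The documents leave open which comparison the 8 per group was meant for:

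- The study title in the IRB letter at the front of the Protocol names one pair of devices: "Fluid Administration with LifeFlow vs Push/Pull".
- The Protocol's Training section describes a third device, under the entry "For Pressure Bag".
- The SAP reports two kinds of analysis. One is "Differences between 2 groups were also evaluated by comparison of median and mean differences with their associated 95% confidence intervals (CIs"; the other is "Comparisons involving 3 groups were made with 1-way ANOVA or Kruskal-Wallis tests".
- The SAP says that a P value threshold of .05 "was considered to be significant throughout". Two-tailed testing is mentioned only for categorical variables.

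**The concern.** Power is the probability of detecting the target difference if it exists. At 0.08 the trial would miss a true 3 mL/s difference 92 times in 100 (1 − 0.08 = 0.92), only slightly better than the 0.05 rejection rate when the devices do not differ. Nobody sizes a trial to that target, so the printed figure contradicts the purpose of its own sentence.

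At stake is the trial's sample-size justification. A reader who takes the figure literally would conclude that the trial was almost incapable of finding its target difference, and would discount any non-significant device comparison. A reader who suspects a misprint cannot confirm the right value, because the inputs that would settle it are not stated.

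**Working it through.** **Inputs from the SAP.** n = 8 teams per group; difference δ = 3 mL/s; alpha = 0.05; printed power 0.08; 9 per group enrolled in 3 groups (3 × 9 = 27).

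**Inputs not given.** SD, test, sidedness and comparison. Without an SD, neither the 8 per group nor the 0.08 can be reproduced. The check instead solves each standard formula for the SD that n = 8, δ = 3 and alpha = 0.05 would require.

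**Formulas.**

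- Two-group t-test: noncentral t with 2n − 2 = 14 degrees of freedom and noncentrality δ / (SD × √(2/n)). With n = 8, √(2/8) = 0.5, so this is 6/SD.
- Three-group one-way ANOVA: noncentral F with 2 and 3(n − 1) = 21 degrees of freedom and noncentrality n × Σ(μᵢ − μ̄)² / SD². For means (0, δ/2, δ) the sum of squares is δ²/2. For means (0, 0, δ) it is 2δ²/3.
- Normal approximation: SD = δ × √(n/2) / (z for alpha + z for power).

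**Results.** Each formula was solved for the standardised difference d, with SD = 3/d. The last column is the SD range in which 8 is the smallest n reaching 0.80. Its lower end is the SD giving 0.80 at n = 7; its upper end is the SD giving 0.80 at n = 8.

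| Test assumed | SD at power 0.08 (mL/s) | SD at power 0.80 (mL/s) | SD range giving n = 8 at 0.80 (mL/s) |
|---|---|---|---|
| Two-sided t | 3/0.272 = 11.0 | 3/1.507 = 1.99 | 1.84–1.99 |
| One-sided t | 3/0.126 = 23.8 | 3/1.308 = 2.29 | 2.13–2.29 |
| ANOVA, third arm midway | 3/0.332 = 9.0 | 3/1.670 = 1.80 | 1.66–1.80 |
| ANOVA, third arm equal to one extreme | 3/0.288 = 10.4 | 3/1.446 = 2.07 | 1.92–2.07 |
| Normal approximation, two-sided | 3/0.277 = 10.8 | 3/1.401 = 2.14 | 2.00–2.14 |
| Normal approximation, one-sided | 3/0.120 = 25.0 | 3/1.243 = 2.41 | 2.26–2.41 |

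(d is shown rounded; the SDs come from unrounded values.)

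**Simulation check.** With 200,000 simulated two-sided t-tests at n = 8, an SD of 11.03 gives power 0.080 and an SD of 1.99 gives 0.800.

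**What the literal reading would require.** At an SD of 11.03 mL/s, 80% power by two-sided t-test would need 214 teams per group. At smaller SDs, 8 per group gives far more than 0.08: power is 0.96 at SD 1.5, 0.80 at SD 2, 0.46 at SD 3 and 0.20 at SD 5. For any SD of 3 mL/s or less, the normal formula asks for only 1 team per group to reach 0.08. A calculation really aimed at 0.08 would therefore give 8 teams only if the SD were several times the target difference.

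**An alternative reading.** If 0.08 was a type II error rate labelled as power, the power would be 1 − 0.08 = 0.92 and the implied SD 1.66 mL/s (two-sided t) or 1.78 mL/s (two-sided normal). That is also arithmetically possible.

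**The case against.** The strongest reply is that this is a misprint most readers would correct to 0.80 without help, in a paragraph written in the past tense about a study already enrolled. Nothing in conduct or analysis depends on it. That is largely right, and it is why the point is minor.

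Three further objections have some force:

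- **No calculation has been shown to be wrong.** With no SD there is none to contradict. The fault is an implausible printed figure, and every SD above depends on an assumed test.
- **A slip for 0.80 is not the only explanation.** The figure could be a type II error rate, so the diagnosis can only be called probable.
- **Printing 0.80 would not by itself let a reader check the 8 per group.** The SD, test and comparison would still be needed. This argues for supplying them in the same correction, not for leaving the figure alone.

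Text conversion is a weaker explanation. The same paragraph has lost the comparison sign before .05, but a dropped symbol does not readily turn one well-formed number into another. Part of the SAP was not available, so the statement that the inputs are missing applies only to the text seen. The printed 0.08 stands in a complete sentence and is not credible either way.

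**Conclusion.** The concern holds, as a minor fault. As printed, "power=0.08, alpha 0.05" is not a usable justification for 8 teams per group. A slip for 0.80 is the most likely explanation: by t-test or ANOVA it needs an SD of only about 1.8 to 2.3 mL/s, against 9.0 to 23.8 mL/s for the literal figure. The text cannot prove it, and a power of 0.92 is also possible.

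Confidence is high that the printed figure is wrong, and lower about what it should be. The SD figures assume equal groups, a common SD, normally distributed team-level rates and the named test. The conclusion that 0.08 is not a credible design power needs none of these assumptions. It does not follow that the trial's true power was 8%, or that 8 or 9 teams per group was the wrong number.

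**What to change.** Go back to the original calculation and replace the sentence with one that gives the power and every input. Suggested wording, with brackets filled from that calculation:

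> With an SD of [x] mL/s from the abstract, 8 teams per group gives power [value] to detect a 3 mL/s difference between [device pair or pattern of means] using a [sidedness] [test] at alpha 0.05.

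The power should come from the calculation and should not simply be changed to 0.80. Once the SD and test are known, the matching row of the table shows whether 8 per group follows at 0.80. If the calculation used another power, the same formula should be rerun at that value.

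The cost is one sentence of SAP wording. Enrolment, conduct and analysis do not change.
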